### *Cold challenge protocol*

This involves 1 minute's exposure to  $15^{\circ}\text{C}$  water for both hands (in case of DU, only the hand with no DU), and rewarming at an ambient temperature of  $23^{\circ}\text{C}$  ( $\pm 2^{\circ}\text{C}$ ). Immediately prior to the cold challenge, a baseline image of both hands will be taken with the thermal camera with the subject's hands placed on a black, thermally insulated surface. Two standard containers of water at  $15 \pm 1^{\circ}\text{C}$  (measured by thermometer) will be prepared and placed on either side of the subject. Both hands will then be gloved and immersed for 1 minute in the cooled water. The hands will be submerged to the metacarpophalangeal joints. After the cold challenge, the gloves will be removed, and the hands returned to their original position on the insulating surface. Reperfusion/rewarming after cold challenge will be imaged simultaneously during the 15 minutes following hand removal from the water. Thermography images will be captured at 4 frames per minute (to allow faster changes to be observed than at slower rates). At the end of the 15 minutes one extra image will be taken to allow the gradient of the last data point to be calculated; thus, a total of 61 images/scans are obtained for both assessments during the 15 minutes of measurement.

### *Thermography*

Thermography images will be securely transferred electronically to the University of Manchester for automated analysis. The region of interest is defined as 2 dorsal regions: one on the dorsum of each hand and all 8 distal phalanges (excluding thumbs). At baseline before cooling, a distal dorsal difference (DDD) is defined for all 4 fingers on each hand in relation to the dorsum of the same hand (4 values for each hand, i.e., 8 in total). These are then averaged to give one DDD per hand or one for both hands. During and after cold challenge only the fingers are assessed. At each time point, the value for the 8 fingers can be plotted individually, but the areas under the curve (AUC) and maximum values are averaged for all 8 fingers. Thus, providing one DDD and one AUC and MAX per subject per cold challenge. This will be performed in a semi-automated way using software (based on observer-defined regions).

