### 4.2 Exclusion Criteria

Individuals who meet any of the following criteria are not eligible to participate in the study.

1. SSc disease duration of greater than 120 months from first non-Raynaud manifestation
2. Current smokers or stopped smoking or used nicotine in any form  $< 3$  months prior to Visit 1.
3. Dose-change or initiation of vasodilating substances (calcium blockers or PDE-5 inhibitors) within 4 weeks prior to Visit 1. Subjects are not allowed to use a combination of calcium blockers and PDE-5 inhibitors from 4 weeks prior to Visit 1 and throughout the study.

4. Use of iloprost or other intravenous (iv) or po prostacyclin receptor agonist within 4 weeks prior to Visit 1.
5. Ongoing treatment with immunosuppressive therapies (other than mycophenolate) including, but not restricted to; cyclophosphamide, azathioprine, methotrexate, or cyclosporine, or use of those medications within 4 weeks of trial entry.  
*Note: Subjects could be included if they have been treated with a stable dose of mycophenolic acid during 4 weeks prior to Visit 1.*
6. Use of systemic corticosteroids during 4 weeks prior to Visit 1 and during the course of the study.
7. Use of moderate or strong CYP3A4 inhibitors within 5 terminal half-lives or one week, whichever is longer, prior to Visit 2. Examples of a moderate or strong CYP3A4 inhibitors are diltiazem, verapamil and grapefruit juice. See [Appendix 13](#) for more examples.
8. Concurrent serious medical condition, with special attention to cardiovascular conditions, which in the opinion of the Investigator makes the subject not suitable for this study.
9. Prolonged QTcF interval defined as a mean QTcF >450 msec at Visit 1, or at Visit 2 (prior randomisation).
10. Creatinine clearance <50 mL/min (determined by Cockcroft-Gault equation) at Screening (Visit 1).
11. Active digital ulcer (DU) within 4 weeks prior to Visit 1.
12. Have known allergies to any components of the GS-248 formulation.
13. Clinically meaningful laboratory abnormalities at Screening (Visit 1), as determined and documented by the Investigator.
14. Positive test results for HbsAg, HCVAb or HIV-1 and/or -2 antibodies at Screening (Visit 1)
15. Subjects known or suspected of not being able to comply with this trial protocol (e.g. due to alcoholism, drug dependency or psychological disorder).

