- Mean DDD of all eight fingers after IMP administration but prior to cold challenge at visit 2 (MDDDF)

Descriptive statistics of the observed cases and change from baseline will be created for these parameters at pre-IMP (Baseline, Session 1, $t = 80$ to 120 min) and post-IMP (Session 2, $t = 0$ to 150 min).

The analysis of the peripheral blood flow will be similar to the analysis of the primary efficacy endpoint using observed data.

5.3.6 Mean change in recovery of peripheral blood flow after cold challenge from pre-IMP to post-IMP administration at Visit 2

The following parameters for recovery of peripheral blood flow after cold challenge from pre-IMP to post-IMP administration are defined:

- Recovery of peripheral blood flow, in terms of mean LN(AUC temp at all eight fingers after cold challenge and after IMP administration) at Visit 2. (Session 2, LN(MAUC8))
- Mean LN(maximum temperature of all eight fingers after cold challenge and after IMP administration) at Visit 2. (Session 2, LN(MMAX8))

After summarizing the log-transformed values, the back-transformed values of the descriptive statistics of the log-transformed values and of the descriptives of the changes on log-scale will be created for these parameters at pre-IMP (Baseline, Session 1) and post-IMP (Session 2).

Statistical Analysis Plan	Version 2.0		Page 23 of 24
Sponsor	Gesynta Pharma AB	Protocol No	GS-2001

The analysis of the peripheral blood flow will be similar to the analysis of the primary efficacy endpoint using observed data.

5.3.7 Mean change from baseline to week 4 in recovery of peripheral blood flow after cold challenge.

The following parameters for recovery of peripheral blood flow after cold challenge are defined:

- Recovery of peripheral blood flow, in terms of mean LN(AUC temp all eight fingers after cold challenge) at visit 4.
- Mean LN(maximum temperature of all eight fingers after cold challenge) at Visit 4.

After summarizing the log-transformed values, the back-transformed values of the descriptive statistics of the log-transformed values and of the descriptives of the changes on log-scale will be created for these parameters at pre-IMP (Baseline, Session 1) and post-IMP (Visit 4).

The analysis of the peripheral blood flow will be similar to the analysis of the primary efficacy endpoint using observed data.

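### With a digital ulcer only one hand is cooled, but the cold-challenge recovery endpoints average all eight fingers and have no rule for the uncooled hand

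*Protocol*

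**What the plan says.** **Which hands are cooled.** Protocol Appendix 5 (cold challenge protocol) opens with both hands exposed to the water, but "in case of DU, only the hand with no DU". Further on, the same paragraph says "Both hands will then be gloved and immersed for 1 minute in the cooled water", without repeating the exception.

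**Which fingers are averaged.** Appendix 5 (thermography) takes the distal phalanges of all eight fingers as the region of interest and says that "the areas under the curve (AUC) and maximum values are averaged for all 8 fingers". It concludes: "Thus, providing one DDD and one AUC and MAX per subject per cold challenge". A per-hand result is allowed only for the distal dorsal difference measured before cooling.

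**The SAP.** Section 5.3.6 (pre- to post-dose at Visit 2) analyses the natural log of the "AUC temp at all eight fingers after cold challenge and after IMP administration". Section 5.3.7 (baseline to week 4) uses the "AUC temp all eight fingers after cold challenge". Both sections treat the maximum in the same way, and the variable names in 5.3.6 (MAUC8, MMAX8) carry the eight. SAP Appendix 2 adds that there are no derivation details beyond sections 5 to 7.

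**Who can be affected.** Exclusion 11 covers "Active digital ulcer (DU) within 4 weeks prior to Visit 1". The only extra exclusion for the cold challenge is finger temperature at Visit 2. DU status is noted at each visit, but neither document links it to the thermography derivation.

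**The concern.** The recovery endpoints are meant to measure how well cooled fingers rewarm. A hand that was never in the water has nothing to recover from and stays near its pre-cooling temperature. Averaging its four fingers with the four cooled ones produces a value that looks like better recovery, and the subject concerned has an ulcer. If the ulcer is present at only one of two visits, the change score also compares unlike quantities.

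At stake are the two post-challenge recovery endpoints in SAP 5.3.6 and 5.3.7. The blood-flow measures taken before cooling, the primary endpoint and the key secondary endpoints are not touched.

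**Working it through.** **1. Can the case arise?** Exclusion 11 stops at Visit 1. Visit 1 falls on Day -21 to -14 and Visit 4 on Day 26 to 29. With no Day 0 (SAP 4.1.3), the gap to Visit 4 is 14 + 25 = 39 to 21 + 28 = 49 days. An ulcer arising in that time does not bar the challenge, and the one-hand clause provides for it.

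**2. Image count.** Four frames a minute for 15 minutes plus one extra gives 15 × 4 + 1 = 61, which matches Appendix 5.

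**3. Inflation of one eight-finger AUC.** Let A be the mean AUC of the cooled fingers and U that of the uncooled fingers. The literal rule returns (A + U)/2 in place of A. On the SAP's log scale the inflation is LN[(A + U)/(2A)].

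The documents give no rewarming data, so all temperatures here are assumptions. The uncooled hand stays at the pre-cooling temperature b. The cooled fingers start at c and regain a fraction f of the drop by 15 minutes, rewarming exponentially at 0.2 per minute. The lowest b used, 27°C, is the protocol's own finger-temperature threshold for the challenge.

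| Case | b, c (°C), f | A | U | (A + U)/2 | LN inflation |
|---|---|---|---|---|---|
| Smallest | 27, 24, 1.0 | 392 | 405 | 399 | 0.016 |
| Central | 30, 21, 0.5 | 364 | 450 | 407 | 0.112 |
| Largest | 33, 18, 0 | 270 | 495 | 382 | 0.348 |

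AUC is in °C·min. In the central case the AUC is 12% too high and the maximum reads 27.8 instead of 25.5°C (9% too high). Over the full grid (b 27 to 33, c 18 to 24, f 0 to 1) the maximum is inflated by 0% when recovery is complete and by up to 42% when there is none. The false credit to the maximum is therefore largest where true recovery is poorest.

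**4. Direction of the change score.**

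| Endpoint | Ulcer present | Effect on LN(AUC) change |
|---|---|---|
| 5.3.7 | Visit 4 only | too high by 0.016 to 0.348 |
| 5.3.7 | Visit 2 only | too low by the same range |
| 5.3.7 | both visits, same hand | diluted |
| 5.3.6 | Visit 2 (both sessions, same day) | diluted |

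For dilution, suppose the cooled hand truly improves from half to full recovery (b = 30, c = 21) and the uncooled hand does not change. The true change is LN(412.1/363.5) = 0.125. The literal rule gives LN(431.0/406.8) = 0.058, a little under half.

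**5. Effect on an arm mean.** About 50 subjects are planned for the cold challenge (Protocol 8.10), so about 25 per arm if split equally. One subject affected at a single visit shifts the arm's mean LN(AUC) change by 0.016/25 = 0.0006 to 0.348/25 = 0.014; the central value is 0.112/25 = 0.0045. No SD is given for this endpoint, so the shift cannot be turned into power or type I error.

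**The case against.** The strongest reply is that the plan never instructs anyone to score an uncooled hand. Appendix 5 does not describe imaging after a one-hand challenge, and reading is semi-automated with regions set by an observer, so a reader could leave that hand out. The later sentence on immersing both hands, taken alone, leaves no hand uncooled. SAP 2.3 also lets the blinded review identify excluded data values. And the stakes are low: the objectives tables call these endpoints secondary, but SAP 5.3 analyses them as exploratory with nominal p-values.

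Much of this stands. Inclusion of the uncooled hand is the literal result of the rule, not a stated intention, and the low stakes are accepted. What does not stand is that the gap closes itself. SAP Appendix 2 rules out further derivation details, and no rule tells the reader which hand was cooled. A reader who used four fingers on their own initiative would still leave a change score comparing eight fingers with four.

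A reader might go further and infer that the error generally favours apparent recovery, or favours the arm with more ulcers. The documents do not support that. The sign depends on when the ulcer is present. The one-visit mechanism cannot apply to 5.3.6, where both sessions are on the same day. A between-arm bias needs ulcers to differ by arm. Nor do the documents show that ulcers are expected in any number: the one-hand clause is a contingency, and exclusion 11 removes recent cases.

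**Conclusion.** The point holds as an inconsistency between procedure and derivation. Applied as written, the eight-finger rule gives a wrong recovery value for any subject who has only one hand cooled, and nothing in either document removes it. The two statements in Appendix 5 on which hands are immersed also conflict; the sponsor must reconcile them, and no view is taken here on which is right.

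The practical effect is probably small. Few subjects are likely to be affected, and even the largest assumed case moves an arm's mean by about 0.014 on the log scale per affected subject. That size rests on assumed temperatures, an uncooled hand that stays constant, and 25 subjects per arm. How many subjects are affected, and whether the shift matters against the endpoint's variability, cannot be settled from the documents. This is a worthwhile clarification and no threat to the trial's main conclusions.

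**What to change.** In Protocol Appendix 5 and SAP 5.3.6 and 5.3.7:

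- State that only fingers of an immersed hand enter the AUC and maximum.
- Compute each change score from the hand or hands immersed at both sessions being compared.
- If no hand was immersed at both sessions (for example, different hands at Visits 2 and 4), set the change to missing under the existing observed-data rule.
- Record the immersed hand(s) for each session in the eCRF and pass this to the central reader.
- Reconcile the two Appendix 5 statements on immersion. The derivation rule works under either: if both hands are always immersed, it changes nothing.

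The cost is a short addition to the SAP and the reading instructions, plus one eCRF field per session. The few affected subjects would have slightly noisier four-finger means or an occasional missing value. All other subjects' values stay as they are.

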## **APPENDIX 6: MICROVASCULAR VOLUME**

Microvascular volume will be assessed at the nailfold of the third finger of the dominant hand, at the proximal phalanx of the same finger and dorsum of the dominant hand. For the purpose of Microvascular volume assessment, subjects will undergo D-OCT scan using VivoSight scanner equipped with a 20-kHz swept-source laser and D-OCT processing software (Michelson Diagnostics, Kent, UK).

Each scan includes 500 frames with a width of 3 mm and will last approximately 60 seconds. The capillary pattern will be visualised in horizontal D-OCT images (“en-face view”).

All the D-OCT images will be collected by a delegated member of staff previously trained, and subsequently analysed by the built-in software tool (Michelson Diagnostics Ltd.) ([Themstrup et al; 2016](#)). The “flow at depth” signal will be measured until the peak and extracted from each D-OCT scan, quantified as area under the curve and defined as “MicroVascular Volume” (MVV).

## **APPENDIX 7: NAILFOLD CAPILLAROSCOPY**

Nailfold capillaroscopy is a technique used routinely to assess the degree of microvascular abnormality in subjects with SSc. It involves examining the small blood vessels (capillaries) in the skin at the base of the fingernail.

It is anticipated that all participating centres will have their own nailfold capillaroscopy system as this technique is routinely used for SSc diagnosis in all centers.

At Visit 1 (could be performed at Visit 2 if the assessment was not feasible at Visit 1), after a period of 20 minutes' acclimatisation at standard room temperature, preferably all 8 fingers (thumbs excluded) will be assessed, and images (up to 4 images taken at each nailfold; 2 from either side of midline) will be stored for potential subsequent analysis.

The investigator will assess the capillaroscopy pattern as 'normal', 'early', 'active' or 'late' ([Herrick AL and Cutolo M, 2010](#)).

Images will be securely transferred to University of Manchester for potential automated analysis of capillary density and dimension.

**APPENDIX 8: METHODS OF ASSESSMENT FOR EFFICACY ENDPOINTS**

Assessment	Description	Evaluation	Visit	Method of Collection
RP attack (eDiary)	A PRO Number and duration of attacks (for each attack: date, start time, stop time). Pain NRS for each attack.	-Mean number of RP attack during 7 days prior to Visit 4 compared with the mean number of RP attacks 7 days prior to Visit 2. -Cumulative duration of RP attacks during 7 days prior to Visit 4 minus the cumulative duration of RP attack during 7 days prior to Visit 4. - Mean change in NRS during 7 days prior to Visit 4 minus the mean NRS during 7 days prior to Visit 2	Daily from Visit 1 through to Visit 5	eDiary
Raynaud's Condition Score (RCS)	A PRO RCS is a validated numeric rating scale 0-10 (0 = No difficulty; 10 = Extreme difficulty) answering the question "What difficulty did you have today with your Raynaud's condition". To measure disease activity and Functional status	Mean score during 7 days prior to Visit 4 compared with mean score during 7 days prior to Visit 2.	Daily from Visit 1 through to Visit 5	eDiary
Physician Global Impression of Change	The clinician is answering the question "Considering all the ways in which Raynaud's symptoms affect your patient, compared to the start of treatment, how do you rate your patient's Raynaud's?" using a scale of; 1 = much better, 2 = a little better, 3 = no change, 4 = a little worse, 5= much worse.	The score at Visit 4 to be used	Visit 4	eCRF
Patient Global Impression of Change	A PRO The subject is answering the question "Considering all the ways in which Raynaud's symptoms affect you, compared to the start of treatment, how do you	The score at Visit 4 to be used	Visit 4	eDiary

Assessment	Description	Evaluation	Visit	Method of Collection
	rate your Raynaud's currently?" using a scale of; 1 = much better, 2 = a little better, 3 = no change, 4 = a little worse, 5 = much worse.			
ASRAP Questionnaire	A PRO	A newly developed outcome measure to assess the impact of RP physically and mentally, and how it impacts on subjects' daily life.	Visit 2 Visit 3 Visit 4 Visit 5	Paper
Nailfold capillaroscopy	Nailfold capillaroscopy on 4 fingers on each hand according to a standardised method to assess severity of the micro vasculopathy.	Baseline evaluation of severity of condition, including classification into designated patterns (normal, early, active, late). Pictures will also be captured and sent for central reading with automated analysis which will compute density and size.	Visit 1 (or Visit 2 pre-randomization)	Central reader (density and width) - eCRF (vasculopathy)
Assessments conducted at pre-selected sites				
Peripheral vascular blood flow before cold challenge	Thermography Images will be obtained before first cold challenge at Visit 2 and before IMP is administered at Visit 4.	Change in peripheral blood flow from first assessment at Visit 2, to assessed before IMP administration at Visit 4.	Visit 2 Visit 4	Thermography images by central reader - eCRF
Peripheral vascular blood flow post IMP dose	Thermography images will be obtained in accordance with SoA.	Change in peripheral blood flow from before IMP to after IMP on Visit 2	Visit 2	Thermography images by central reader - eCRF
Peripheral vascular blood flow after cold challenge	Reperfusion/rewarming following the cold challenge will be imaged by thermography every 15 seconds (4 frames per minute), for 15 minutes.	Change in recovery of peripheral blood flow after cold challenge	Visit 2 (Session 1) Visit 2 (Session 2)	Thermography images by central reader - eCRF
Peripheral vascular blood flow after cold challenge	Reperfusion/rewarming following the cold challenge will be imaged by thermography every 15 seconds (4 frames per minute), for 15 minutes.	Change in recovery of peripheral blood flow after cold challenge from Visit 2 to Visit 4	Visit 2 (Session 1) Visit 4	Thermography images by central reader - eCRF

Assessment	Description	Evaluation	Visit	Method of Collection
Microvascular volume	Dynamic Optical Coherence Tomography (D-OCT) assessment of skin/nailfold		Visit 2 Visit 3 Visit 4 Visit 5	Equipment at site (eCRF)
Blood samples				
PK sparse			Visit 2 Visit 3 Visit 4	Central lab Lablytica
Biomarkers for inflammation and endothelium dysfunction	hsCRP, endothelin-1, sE-selectin, ICAM1, TNF, IL-1b, IL-4, IL-6, IL-10, s-PECAM1 CXCL-4, CD40L, and von Willebrand factor.		Visit 2 Visit 4	Central laboratory
Potential future analysis of inflammatory biomarkers and endothelial dysfunction.			Visit 2 Visit 4	Central laboratory (KI Biobank)
Blood samples conducted at pre-selected sites				
PK rich			Visit 4	Central lab Lablytica
PGE 2 levels in whole blood			Visit 2 Visit 4	Central lab Lablytica
Expression of platelet surface markers	FACS analysis		Visit 2 Visit 4	Local laboratory
Urine samples				
AA-metabolites (PGEM, PGIM, TXM)	Subjects will bring a urine sample (first urination of the morning).		Visit 2 Visit 4	Central lab Lablytica
Potential future analysis of inflammatory biomarkers and endothelial dysfunction			Visit 2 Visit 4	Central lab (KI Biobank)

## APPENDIX 9: DEFINITIONS OF DIAGNOSES

### The American College of Rheumatology/European League Against Rheumatism criteria for the classification of systemic sclerosis (SSc)\*

Item	Sub-item(s)	Weight/score †
Skin thickening of the fingers of both hands extending proximal to the metacarpophalangeal joints (sufficient criterion)	-	9
Skin thickening of the fingers (only count the higher score)	Puffy fingers	2
	Sclerodactyly of the fingers (distal to the metacarpophalangeal joints but proximal to the proximal interphalangeal joints)	4
Fingertip lesions (only count the higher score)	Digital tip ulcers	2
	Fingertip pitting scars	3
Telangiectasia	-	2
Abnormal nailfold capillaries	-	2
Pulmonary arterial hypertension and/or interstitial lung disease (maximum score is 2)	Pulmonary arterial hypertension	2
	Interstitial lung disease	2
Raynaud's phenomenon	-	3
SSc-related autoantibodies (anticentromere, anti-topoisomerase I [anti-Scl-70], anti-RNA polymerase III) (maximum score is 3)	Anticentromere	3
	Anti-topoisomerase I	
	Anti-RNA polymerase III	

Adapted from Van den Hoogen F, et al. *Arthritis & Rheumatism*, 2013;65(11):2737-47.

\* These criteria are applicable to any patient considered for inclusion in an SSc study. The criteria are not applicable to patients with skin thickening sparing the fingers or to patients who have a scleroderma-like disorder that better explains their manifestations (e.g., nephrogenic sclerosing fibrosis, generalised morphea, eosinophilic fasciitis, scleredema diabeticorum, scleromyxedema, erythromyalgia, porphyria, lichen sclerosis, graft-versus-host disease, diabetic cheiroarthropathy).

† The total score is determined by adding the maximum weight (score) in each category. Patients with a total score of  $\geq 9$  are classified as having definite SSc.

